10.6.4. Reporting of SAE to VH/GSK

SAE Reporting to VH/GSK via Electronic Data Collection Tool

- The primary mechanism for reporting SAE to VH/GSK will be the electronic data collection tool.
- If the electronic system is unavailable, then the site will use the paper SAE data collection tool (see next section) in order to report the event within 24 hours.
- The site will enter the SAE data into the electronic system as soon as it becomes available.
- The investigator or medically-qualified sub-investigator must show evidence within the electronic CRF (e.g., check review box, signature, etc.) of review and verification of the relationship of each SAE to study intervention/study participation (causality) within 72 hours of SAE entry into the electronic CRF.
- After the study is completed at a given site, the electronic data collection tool will be taken off-line to prevent the entry of new data or changes to existing data.
- If a site receives a report of a new SAE from a study participant or receives updated data on a previously reported SAE after the electronic data collection tool has been taken off-line, then the site can report this information on a paper SAE form (see next section) or to the medical monitor by telephone.
- Contacts for SAE reporting can be found in the SRM.

SAE Reporting to VH/GSK via Paper CRF

- Facsimile transmission of the SAE paper CRF is the preferred method to transmit this information to the medical monitor.
- In rare circumstances and in the absence of facsimile equipment, notification by telephone is acceptable with a copy of the SAE data collection tool sent by overnight mail or courier service.
- Initial notification via telephone does not replace the need for the investigator to complete and sign the SAE CRF pages within the designated reporting time frames.
- Contacts for SAE reporting can be found in SRM.

10.7. Appendix 7: Genetics

USE/ANALYSIS OF DNA

- Genetic variation may impact a participant's response to study intervention, susceptibility, severity, and progression of disease. Variable response to study intervention may be due to genetic determinants that impact drug absorption, distribution, metabolism, and excretion; mechanism of action of the drug; disease etiology; and/or molecular subtype of the disease being treated. Therefore, where local regulations and IRB/IEC allow, a blood sample will be collected for DNA analysis.
- DNA samples will be used for research related to GSK3640254 or HIV and related diseases. They may also be used to develop tests/assays including diagnostic tests related to GSK3640254 or HIV MIs and HIV. Genetic research may consist of the analysis of 1 or more candidate genes or the analysis of genetic markers throughout the genome or analysis of the entire genome (as appropriate).
- DNA samples will be analyzed if it is hypothesized that this may help further understand the clinical data.
- The samples may be analyzed as part of a multi-study assessment of genetic factors involved in the response to GSK3640254 or study interventions of this class. The results of genetic analyses may be reported in the clinical study report or in a separate study summary.
- The sponsor will store the DNA samples in a secure storage space with adequate measures to protect confidentiality.
- The samples will be retained while research on GSK3640254 (or study interventions of this class) or HIV continues but no longer than 15 years after the last participant's last visit or other period as per local requirements.

1. INTRODUCTION

The purpose of this reporting and analysis plan (RAP) is to describe the analyses to be included in the Clinical Study Report for Protocol: 209712

2. SUMMARY OF KEY PROTOCOL INFORMATION

This is an open-label, single-sequence, two-way drug interaction study to investigate the pharmacokinetic (PK) interactions between GSK3640254 and dolutegravir (DTG). Treatment of human immunodeficiency virus (HIV) infection frequently involves combination therapy. It is important to understand any interactions and resulting changes in exposure (if any) when HIV medications are given in combination. Data from this study will contribute to dosing recommendations when GSK3640254 and DTG are given in combination.

[figure not shown]
2.1. Changes to the Protocol Defined Statistical Analysis Plan

There were no changes or deviations to the originally planned statistical analysis specified in the protocol (Dated: 12/DEC/2018).

2.2. Study Objective(s) and Endpoint(s)

Ob	jectives	En	dpoints
Pri	Primary Objectives		mary Endpoints
•	To assess the effect of GSK3640254 on the steady state PK of DTG under fed conditions in healthy participants	•	Area under the plasma concentration-time curve (AUC) from time 0 to the end of the dosing interval at steady state [AUC(0- τ)], maximum observed concentration (Cmax), and plasma concentration at the end of the dosing interval (C τ) for DTG
•	To assess the effect of DTG on the steady state PK of GSK3640254 under fed conditions in healthy participants	•	AUC(0- τ), Cmax, and C τ for GSK3640254
Se	condary Objectives	Se	condary Endpoints
•	To assess the safety and tolerability of GSK3640254 and DTG administered alone and when given in combination in healthy participants	•	Safety and tolerability parameters for adverse events (AEs)/serious AEs (SAEs), observed and change from baseline clinical laboratory assessments, electrocardiograms (ECGs), and vital sign measurements
•	To characterize the steady state PK of GSK3640254 alone and when given in combination with DTG under fed conditions in healthy participants	•	Time of maximum observed concentration (Tmax) and apparent terminal phase half-life (t1/2) for GSK3640254
•	To characterize the steady state PK of DTG alone and when given in combination with GSK3640254 under fed conditions in healthy participants	•	Tmax and t1/2 for DTG

2.3. Study Design

2.4. Statistical Hypotheses

No formal hypotheses will be statistically tested for this study.

Analyses will be performed to assess the effect of GSK3640254 on the PK of DTG, and the effect of DTG on the PK of GSK3640254, as appropriate.

Analyses will be performed on the natural logarithms of the primary plasma PK parameters (AUC(0- τ), C τ , and Cmax) using linear mixed-effect models with period as a

fixed effect and measurements within participant as repeated measures. Effects will be estimated, and confidence intervals (CIs) will be constructed for the following treatment comparisons:

- Period 3 versus Period 1 (DTG)
- Period 3 versus Period 2 (GSK3640254)

3. PLANNED ANALYSES

3.1. Final Analyses

The final planned primary analyses will be performed after the completion of the following sequential steps:

- 1. All participants have completed the study as defined in the protocol.
- 2. All required database cleaning activities have been completed and final database release (DBR) and database freeze (DBF) has been declared by Data Management.

4. ANALYSIS POPULATIONS

Population	Definition / Criteria	Analyses Evaluated
Screened	All participants who signed the informed consent form	 Study Population
Safety	 All participants who received at least 1 dose of study medication. This population will be used for all demographic and safety summaries 	Study PopulationSafety
Pharmacokinetic Concentration	 All participants who underwent plasma PK sampling and had evaluable PK assay results. This population will be used for the PK concentration listings, summary tables, and plotting of concentration-time data. 	PK Concentration
Pharmacokinetic Parameter	 All participants who underwent plasma PK sampling and had evaluable PK parameters estimated. This population will be used for PK parameter listings, summary tables, and statistical analysis tables. 	PK ParameterPK statistical analysis

Refer to Appendix 9: List of Data Displays which details the population used for each display.

4.1. Protocol Deviations

Significant protocol deviations (including deviations related to study inclusion/exclusion criteria, conduct of the trial, participant management or participant assessment) will be summarised and listed.

Protocol deviations will be tracked by the study team throughout the conduct of the study in accordance with the Protocol Deviation Management Plan dated 12FEB2019.

- Data will be reviewed prior to freezing the database to ensure all significant deviations and deviations which may lead to exclusion from the analysis are captured and categorised on the protocol deviations dataset.
- This dataset will be the basis for the summaries and listings of protocol deviations.

A separate listing of all inclusion/exclusion criteria deviations will also be provided. This listing will be based on data as recorded on the inclusion/exclusion page of the electronic case record form (eCRF).

5. CONSIDERATIONS FOR DATA ANALYSES AND DATA HANDLING CONVENTIONS

5.1. Study Treatment & Sub-group Display Descriptors

Treatment Group Descriptions				
Data Displays for Reporting				
Description	Code	Order in TLF		
DTG 50 mg QD on Days 1 through 5 in Period 1	DTG 50 mg	1		
GSK3640254 200 mg QD on Days 1 through 7 in Period 2	GSK3640254 200 mg	2		
DTG 50 mg QD + GSK3640254 200 mg QD on Days 1 through 7 in Period 3	DTG 50 mg + GSK3640254 200 mg	3		

5.2. Baseline Definitions

For all endpoints (except as noted in baseline definitions), the baseline value will be the latest pre-dose assessment with a non-missing value, including those from unscheduled visits. If time is not collected, Day 1 assessments are assumed to be taken prior to first dose and used as baseline. Baseline definitions in the tables below are applicable to each period.

Parameter	Study Asses	Baseline Used in			
	Screening	Day -1	Day 1 (Pre-Dose)	Data Display	
Safety					
Vital Sign	X	X	Х	Day 1 (Pre-Dose)	
12-Lead ECG	Х	Х	Х	Day 1 (Pre-Dose)[1]	

^[1] Baseline for 12-lead ECGs are applied to each period. The average (for quantitative assessments) or the worst case (for interpretation) of the predose triplicate assessments on Day 1 of Period 1 will be used as the baseline for Period 1. The average (for quantitative assessments) or the worst case (for interpretation) of the predose triplicate assessments on Day 1 of Period 2 will be used as the baseline for Period 2.

Parameter	Study A	Baseline Used in		
	Day -1	Period 1 Day 9	Period 2 Day 7	Data Display
Safety				
Hematology, Clinical Chemistry, Urinalysis	Х	X	X	Day -1 for Period 1; Period 1 Day 9 for Period 2; Period 2 Day 7 for Period 3

Unless otherwise stated, if baseline data is missing no derivation will be performed and baseline will be set to missing.

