1.2. Schema

A summary of the overall study design is presented in [Figure 1](#).

Figure 1 Study Design Schematic**1.3. Schedule of Activities (SoA)**

- Screening procedures may be done over more than 1 visit but must all be completed within 28 days prior to the first dose of study intervention.
- The following demographic parameters will be captured: year of birth, sex, race, and ethnicity.
- Medical/medication/family history will be assessed as related to the inclusion/exclusion criteria.

Screening Visit

Procedure	Screening (up to 28 days before Day 1)
Outpatient visit	X
Informed consent	X
Inclusion and exclusion criteria	X
Demography	X
Full physical examination including height and weight ¹	X
Laboratory assessments (hematology, chemistry, urinalysis)	X
12-lead electrocardiogram	X
Vital sign measurements	X
Medication/drug/alcohol history	X
Past and current medical conditions	X
Columbia Suicide Severity Rating Scale	X
Serum pregnancy test	X
Follicle-stimulating hormone (as needed, to confirm postmenopausal status)	X
Drug, alcohol, and cotinine screen	X
HIV, Hepatitis B and C screening	X

HIV = human immunodeficiency virus.

1 A full physical examination will include at a minimum, assessments of the skin, cardiovascular, respiratory, gastrointestinal, and neurological systems.

Procedure	Period 1		W	Period 2			Period 3							Follow-up				Notes	
	Day -1	Day 1-5	Day 6-9	Day 1-5	Day 6	Day 7	Day 1	Day 2	Day 3	Day 4	Day 5	Day 6	Day 7	Day 8	Day 9	Day 10 ¹	Day 11		
Admit to clinic	X																		
Discharge from clinic																		X	
Brief physical examination	X																X		A brief physical examination will include, at a minimum, assessments of the skin, lungs, cardiovascular system, and abdomen (liver and spleen).
Vital sign measurements	X	X		X	X	X	X	X	X	X	X	X	X	X	X	X	X	X	
12-Lead ECG	X	D1 and D5		D1 and D5			X			X	X		X				X		All ECGs in Period 1-3 will be pre-dose, post-dose at 2 hours, and post-dose at 4 hours. The predose ECGs on Day 1 of both Period 1 and Period 2 will be taken in triplicate.
Drug, alcohol, and cotinine screen	X																		See Appendix 2 for specific tests to be performed.
Laboratory assessments (hematology, chemistry, urinalysis)	X		D9			X				X			X				X		See Appendix 2 for specific tests to be performed.
Pregnancy test	X																X		
Columbia Suicide Severity Rating Scale				D1									X						
Genetic sample	X																		

Procedure	Period 1		W	Period 2			Period 3							Follow-up				Notes

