4.3. Justification for Dose

The doses of 200 mg GSK3640254 and 50 mg DTG were selected for this study. The maximum projected clinical dose of GSK3640254 is 200 mg QD. The apparent terminal phase half-life (t_{1/2}) of GSK3640254 was approximately 22 hours in the MAD portion of Study 207187 at the 200-mg dose, and predicted time to steady state is approximately 5 days. Dolutegravir 50 mg QD was selected for this study because it is the current recommended dose for HIV-infected patients. The t_{1/2} of DTG is approximately 14 hours, and steady state is generally reached in 3 days.

There is a 4-day washout after DTG alone dosing to eliminate any carryover effect. Dosing of GSK3640254 QD from Days 1 to 7 in Period 2 should be sufficient to bring

plasma concentrations to steady state. There is no subsequent need for a washout of GSK3640254 since the primary remaining evaluation is for coadministered DTG and GSK3640254 at steady state. As GSK3640254 has a longer $t_{1/2}$ than DTG, the time to reach steady state for the coadministered drugs is reduced by the continuation of GSK3640254 dosing.

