8.2.3. Electrocardiograms

- On Day 1 of both Period 1 and Period 2, triplicate ECGs will be taken prior to dosing. The ECGs should be recorded over a brief (e.g., 5 to 10 minutes) recording period. Each measurement will be recorded in the CRF.
- Single 12-lead ECG will be obtained at other time points as outlined in the SoA (Section 1.3) using an ECG machine that automatically calculates the heart rate and measures PR, QRS, QT, and QTcF intervals. Refer to Section 7.1.2 for QTcF withdrawal criteria and additional QTcF readings that may be necessary.
- Twelve-lead ECGs will be performed with the participant in a supine or semi-supine position after a rest of at least 10 minutes.
- At each time point at which triplicate ECG are required, 3 individual ECG tracings should be obtained as closely as possible in succession, but no more than 2 minutes apart. The full set of triplicates should be completed over a brief (e.g., 5 to 10 minutes) recording period.

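### The SAP does not spell out the Period 3 ECG baseline; on its natural reading this is a single tracing at GSK3640254 trough, and no listed display gives the combination's QTcF change from a GSK3640254-free baseline

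*SAP*

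**What the plan says.** SAP 5.2 gives Day 1 pre-dose as the ECG baseline and states that "Baseline definitions in the tables below are applicable to each period". Footnote [1] repeats this for ECGs ("Baseline for 12-lead ECGs are applied to each period") and then gives the detail for two periods only. Period 1 uses its own Day 1 triplicate, and for Period 2 the "predose triplicate assessments on Day 1 of Period 2 will be used as the baseline for Period 2". Period 3 is not named. The laboratory table in the same section does name it: "Day -1 for Period 1; Period 1 Day 9 for Period 2; Period 2 Day 7 for Period 3".

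In the protocol's Schedule of Activities, "The predose ECGs on Day 1 of both Period 1 and Period 2 will be taken in triplicate". Section 8.2.3 adds: "Single 12-lead ECG will be obtained at other time points as outlined in the SoA". On scheduled dosing days ECGs are taken pre-dose and at 2 h and 4 h: Days 1 and 5 in Periods 1 and 2, and Days 1, 4, 5 and 7 in Period 3. Protocol 4.3 runs GSK3640254 straight from Period 2 into Period 3: "There is no subsequent need for a washout of GSK3640254".

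The displays concerned are Table 2.15 (ECG change), Table 2.17 (maximum QTc increase by category) and Figure 2.1 (mean QTcF change with 95% CI, by time point and treatment). Their programming notes in SAP Appendix 9 are blank. SAP 10.7.1 divides QTc increases at 30 and 60 msec. Protocol 7.1.2 bases its QTcF criteria on an averaged Day 1 pre-dose triplicate without naming the period.

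**The concern.** Three columns headed as change from baseline would not measure the same thing. For DTG alone and GSK3640254 alone, the reference is a triplicate average with no GSK3640254 on board. For the combination, on the natural reading, it is one tracing with GSK3640254 near its steady-state trough. The combination column then shows the increment over that trough and leaves out any GSK3640254 effect already present there.

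This matters because protocol 2.3 names QTc prolongation among three major risks of GSK3640254. A secondary objective is also the safety of the two drugs alone and together, with ECG change from baseline as an endpoint. Treatment C is where a reader would look for the combination's QTcF change. A hypothetical participant who is 25 msec up at the Period 3 pre-dose ECG and 20 msec further up after dosing has a total change of 25 + 20 = 45 msec, but would be counted at or below 30 msec under Treatment C.

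**Working it through.** **1. Which ECG is the Period 3 baseline?** Footnote [1] is silent, so the general rule applies: Day 1 pre-dose of that period. The Schedule of Activities marks an ECG on Period 3 Day 1, and triplicates exist only on Day 1 of Periods 1 and 2. The baseline is therefore one tracing. The explicit on-drug laboratory baseline for Period 3 supports this reading. It remains an inference.

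**2. The plan's own figure.** Protocol 4.3 says that the half-life "was approximately 22 hours in the MAD portion of Study 207187 at the 200-mg dose" and predicts steady state in about 5 days. Five half-lives are 5 × 22 / 24 = 4.6 days, and 1 − 2^(−120/22) = 97.7% of steady state at 120 h. The figure reproduces.

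**3. Drug on board at each baseline.** After seven doses, the fraction of steady-state trough is 1 − 2^(−168/22) = 99.5%, or 1 − 2^(−168/29) = 98.2% at the upper repeat-dose half-life. At Period 2 Day 1, GSK3640254 is zero. DTG is 120 h past its last dose, which is 120/14 = 8.6 half-lives, or 2^(−120/14) = 0.26% remaining.

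**4. Share of a GSK3640254 effect removed by the baseline.**
- Assumptions: the effect is proportional to concentration without delay, there is one compartment with first-order absorption, and DTG does not change GSK3640254 exposure.
- Inputs: half-life 22 to 29 h and Tmax 3 to 4.5 h, both from the Study 207187 data in protocol 2.2.
- Concentration after n daily doses, at t hours after the last, is proportional to e^(−kt)(1 − e^(−24nk))/(1 − e^(−24k)) − e^(−ka·t)(1 − e^(−24n·ka))/(1 − e^(−24ka)). Here k = ln 2 / half-life, and ka is solved from Tmax, either single-dose or steady-state.
- Share = C(24 h after dose 7) / C(2 h or 4 h after a Period 3 dose).
- Low corner (22 h; single-dose Tmax 3 h, ka 1.261; 2 h ECG on Day 7): 0.881 / 1.690 = 0.52.
- High corner (29 h; steady-state Tmax 4.5 h, ka 0.527; 2 h ECG on Day 1): 1.268 / 1.813 = 0.70.
- Over the whole grid, the share is 0.52 to 0.70 at 2 h and 0.53 to 0.65 at 4 h.

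**5. Why the wide range is used.** With 22 h and the repeat-dose Tmax of 3.8 to 4.3 h alone, the shares are 0.547 to 0.615 (2 h) and 0.538 to 0.569 (4 h). That model gives Day 14/Day 1 Cmax ratios of 1.93 to 1.96, inside the reported 1.9 to 2.3. Its AUC(0-24) ratios of 1.95 to 1.99 fall below the reported 2.2 to 2.6. At 29 h the AUC ratios (2.34 to 2.44) fit and the Cmax ratios (2.32 to 2.38) sit just above their range. Neither end fits both, so the narrow range would be falsely precise.

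**6. Noise.** Let r be between-occasion SD divided by replicate SD (assumed). The SD of change from a single baseline, relative to a triplicate one, is √[(2r² + 2)/(2r² + 4/3)]. This is 1.22 at r = 0, 1.10 at r = 1 and 1.04 at r = 2. It adds noise, not bias.

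**The case against.** **A per-period baseline may be deliberate.** The laboratory table uses an on-GSK3640254 baseline for Period 3, and in an interaction study the increment on adding DTG is a fair question. This stands. The per-period change should be kept, and a reader who concludes that it is wrong goes further than the documents allow.

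**A reader might infer that the displays are unlabelled.** The documents do not show that. SAP 10.9.2 refers to separate shells, which are not included and could carry a footnote. What can be said is that the display list specifies none.

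**A reader might infer that a QTc signal is hidden or that individuals are unprotected.** Neither follows. Protocol 2.3 reports no QTc value above 500 msec and no increase above 60 msec in Study 207187. Absolute QTc values stay visible through Table 2.16 and Listing 28. The only scheduled Day 1 triplicates that protocol 7.1.2 could mean both precede GSK3640254, and a stopping baseline may differ from a display baseline without contradiction.

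**The mean total change can be approximated.** If observed means are tabulated, subtraction gives it, apart from differing completers. The Period 2 Day 5 pre-dose ECG, after four doses (1 − 2^(−96/22) = 95% of steady-state trough), also gives a near-trough change to add. This stands for means. It does not supply a CI for the total or the per-participant increase categories.

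**An earlier reference brings drift.** Period 2 Day 1 lies 7 to 13 days before the Period 3 dosing-day ECGs, in a fixed sequence without placebo. This stands as a cost of the added display.

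**Conclusion.** The point holds as a gap in specification and display. SAP 5.2 leaves the Period 3 ECG baseline to inference. On the natural reading, Treatment C change is an increment over GSK3640254 trough, shown beside two changes from GSK3640254-free triplicates, and no listed display gives the combination's total change or its >30 and >60 msec categories.

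The 52% to 70% share depends on the assumed linear, undelayed effect and unchanged GSK3640254 exposure. It illustrates how much could be subtracted and is not evidence that an effect exists. The documents establish neither a human QTcF effect nor a concentration-QTc relation, so no msec figure is supportable. Primary PK, absolute QTc values and the Period 2 changes are untouched. The correction is worthwhile because it is cheap and concerns a named major risk, but its impact stops at descriptive safety output for about 16 participants.

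**What to change.** 1. In SAP 5.2, state the Period 3 ECG baseline explicitly.
2. Keep the per-period change in Tables 2.15 and 2.17 and Figure 2.1, labelled for Treatment C as the increment on GSK3640254.
3. Add Period 3 QTcF change and increase categories from the Period 2 Day 1 pre-dose triplicate average. Count only ECGs after the Period 3 Day 1 dose, so that no Period 2 tracing enters under Treatment C.
4. Reconcile protocol 7.1.2 and SAP 5.2 on which period's Day 1 is meant. The added display does not settle that question.

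Cost: a short wording change, one derivation and a few extra displays. No new data are needed, because the triplicate is already scheduled. The added displays carry the 7- to 13-day gap and possible time drift, which a footnote should state.
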